3. STUDY DESIGN

This study is a double-blind, randomized, dose-ranging, placebo-controlled multicenter study with four parallel groups. Approximately 25 sites in five European countries (Czech Republic, Hungary, Italy, Spain and Sweden) will be included in the study. The study setting will include academic hospitals and gynecological clinics. The study population is postmenopausal women who report moderate to severe vaginal dryness as their most bothersome symptom in addition to other symptoms and/or signs of postmenopausal vulvovaginal atrophy.

After providing informed consent, potential subjects will be evaluated during the screening period (maximum 30 days) to determine if they are eligible to participate in the study. A screening identification number will be assigned to each eligible subject according to their order of arrival into the study at the Screening visit. Subjects who meet all of the inclusion criteria and none of the exclusion criteria (see Sections 4.1.1 and 4.1.2 of the study protocol) will be randomized into the study at the Baseline visit. A total of 280 subjects will be enrolled and randomly allocated to one of the four treatment groups (0.005%, 0.002%, or 0.0008% estriol vaginal gel or placebo vaginal gel); the allocation to treatment group will be 1:1:1:1. A blocked randomization across the entire study (i.e. all sites as a whole) will be used. Subjects will be assigned a randomization code according to their order of arrival into the study at the Baseline Visit. Initial treatment consists of daily vaginal administration of 1 gram of randomly-assigned estriol gel or placebo gel using the supplied applicator. Placebo gel will be identical in appearance, texture and odor to the estriol vaginal gel products. After 21 days of daily administration, treatment will continue with twice-weekly administration up to Week 12 (i.e., Mondays and Thursdays).

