6.1.4 Determination of Sample Size

A total of 280 female subjects will be enrolled in the study.

The estimates of treatment differences and variability were gained from the results of Study ITFE-2026-C2.

A sample size of 57 in each group will have 90% power to detect a treatment difference for change in severity of vaginal dryness, assuming five categories with proportions in each treatment group as shown in **Table 2** below, using a Wilcoxon rank sum test with a 0.025 one-sided significance level.

Table 2: Assumed Proportions for Wilcoxon Rank Sum Test of Vaginal Dryness

Change in Vaginal Dryness Severity	Proportion in Estriol Vaginal Gel Group	Proportion in Placebo Group
-3	0.189	0.118
-2	0.423	0.196
-1	0.270	0.353
0	0.118	0.333

Change in Vaginal Dryness Severity	Proportion in Estriol Vaginal Gel Group	Proportion in Placebo Group
1	0	0

A sample size of 48 in each group will have 90% power to detect a treatment difference of -0.89 for change in vaginal pH, assuming a common standard deviation of 1.33 using a two-group t-test with a 0.025 one-sided significance level.

A sample size of 24 in each group will have 90% power to detect a treatment difference of 21 for change in proportion of superficial cells, assuming a standard deviation of 26.3 for 0.005% estriol vaginal gel and 14.8 for placebo vaginal gel, using a two-group Satterthwaite t-test with a 0.025 one-sided significance level.

A sample size of 9 in each group will have 90% power to detect a treatment difference of -53 for change in proportion of parabasal cells, assuming a standard deviation of 37.9 for 0.005% estriol vaginal gel and 19.6 for placebo vaginal gel, using a two-group Satterthwaite t-test with a 0.025 one sided significance level.

The largest sample size calculated for a single co-primary endpoint has been considered the sample size required for the whole study, thus, 57 subjects per group are estimated. Accounting for an 18% drop-out rate, and rounding numbers, approximately 70 subjects/group have been finally estimated.

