6.3 Efficacy Analysis

6.3.1 Primary Efficacy Analysis

The four co-primary efficacy variables in this study are:

- Change from Baseline to Week 12 in the severity of vaginal dryness
- Change from Baseline to Week 12 in vaginal pH
- Change from Baseline to Week 12 in the proportion of superficial cells of the vaginal epithelium

- Change from Baseline to Week 12 in the proportion of parabasal cells of the vaginal epithelium

The planned analyses of each of these four endpoints and the gatekeeping procedure to be employed for obtaining conclusions are described in **Sections 6.3.1.1 to 6.3.1.5** below.

The primary analyses will be performed using the ITT population using LOCF methodology, and confirmatory analyses will be performed using the PP population (using observed data only, since having Week 12 data available is a requirement for inclusion in the PP population). It should be noted that, since the statistical tests are one-sided, only one limit of each confidence interval presented (the limit in the direction where Estriol vaginal gel is favorable for each specific endpoint) is of particular interest for analysis. Each statistical test will examine the null hypothesis that Estriol vaginal gel is no different to Placebo against the alternative hypothesis that Estriol vaginal gel is superior to Placebo.

No adjustment for multiplicity will be made, since statistical significance in all 4 co-primary endpoints is required to declare efficacy. The minimal effective dose will be considered to be the lowest dose at which a significant difference is seen (in favor of Estriol) when compared with Placebo.

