6.3.1.1 Change from Baseline to Week 12 in Severity of Vaginal Dryness

Vaginal dryness is one of the five symptoms of vulvovaginal atrophy, and is self-assessed by the subject at the Screening, Week 3 and Week 12 / Early Termination visits.

Each symptom will be scored by the subject using a numeric scale from 0 to 3, as follows:

0	Absent:	The symptom is not present
1	Mild:	The symptom is of mild intensity
2	Moderate:	The symptom is of moderate intensity
3	Severe:	The symptom is severe in intensity

The number and percentage of subjects with each severity of vaginal dryness at each visit will be summarized by treatment in a general summary table of symptoms of vulvovaginal atrophy.

Given that the Inclusion Criteria for the study require the subject to have moderate (score of 2) or severe (score of 3) vaginal dryness at Baseline (Screening), the change from Baseline to Week 12 may take the possible values ranging from -3 (Severe at Screening; Absent at Week 12) to 1 (Moderate at Screening; Severe at Week 12).

The number and percentage of subjects with each ordinal change from Baseline to Week 12 value (-3, -2, -1, 0 and 1) will be summarized by treatment group.

The change from Baseline to Week 12 in vaginal dryness will be analyzed using a Wilcoxon Rank Sum test, controlled for country, to obtain the one-sided p-values for each treatment

comparison (0.005% Estriol versus placebo, 0.002% Estriol versus placebo and 0.0008% Estriol versus placebo) by means of the FREQ procedure in SAS with the SCORES = RANK option. The Hodges-Lehmann estimate of median difference between treatment groups will also be presented for each of the three treatment comparisons above, along with 95% CIs, by means of the NPAR1WAY procedure in SAS. Hodges-Lehmann estimates will be presented without the adjustment for country, since SAS does not currently produce Hodges-Lehmann estimates when covariates are included. Missing values at Week 12 will be estimated using LOCF methodology for the ITT population analysis only. Only post-Baseline values will be carried forward.

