6.3.1.2 Change from Baseline to Week 12 in Severity of Vaginal pH

A vaginal pH determination will be performed at the Screening, Week 3 and Week 12 / Early Termination visits.

The vaginal pH will be summarized using descriptive statistics for continuous variables by treatment and visit. The change from Baseline (Screening) value will also be summarized for all post-Baseline visits.

The mean change in vaginal pH from Baseline to the Week 12 / Early Termination visit will be analyzed using a parametric analysis of covariance (ANCOVA) model. The model will include treatment and country as fixed effects and the Baseline (Screening) pH will be used as a covariate. The adjusted (least-square) mean (LS Mean) change in vaginal pH from Baseline to Week 12 will be presented for each treatment, along with the corresponding SE. The difference in LS Means between treatment groups (0.005% Estriol versus Placebo, 0.002% Estriol versus Placebo and 0.0008% Estriol versus Placebo) will also be presented with 95% CI and one-sided p-value. The p-values for the model parameters of country and Baseline pH will also be presented. Model assumptions will be examined and, if required, a Wilcoxon Rank Sum test as described for vaginal dryness (Section 6.3.1.1) will be used. Missing values at Week 12 will be estimated using LOCF methodology for the ITT population analysis only. Only post-Baseline values will be carried forward.

6.3.1.3 Change from Baseline to Week 12 in Proportion of Superficial Cells of the Vaginal Epithelium

Vaginal smears will be performed at the Screening, Week 3 and Week 12 / Early Termination visits. Two vaginal smears will be collected per subject at each visit, with one cytological sample sent to the central laboratory [REDACTED] for analysis, and one sample retained at site for backup purposes. The samples sent to [REDACTED] will be evaluated by two different cytopathologists who will be blinded to subject, treatment assignment and to each other's evaluations. The number and percentage of superficial cells will be provided for each pathologist's cytologic evaluation, and the percentages will be converted to proportions for statistical presentation.

The proportion of superficial cells of a given subject and visit to be used for analysis will be derived as the mean result across the two pathologists. The evaluations of both pathologists must be verified by the Clinical Research Associate (CRA) in order to be considered for final analysis.

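### SCORES = RANK in the country-stratified Wilcoxon test for vaginal dryness loses power if countries enrol unequally; with a similar effect across countries, SCORES = MODRIDIT (van Elteren) avoids most of that loss

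*SAP*

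**What the plan says.** Under SAP 6.3.1.1 the change in dryness "will be analyzed using a Wilcoxon Rank Sum test, controlled for country, to obtain the one-sided p-values for each treatment" comparison, "by means of the FREQ procedure in SAS with the SCORES = RANK option". Protocol 7.8.1 also requires control for country but fixes no score.

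On the size of the strata, SAP section 3 says: "Approximately 25 sites in five European countries (Czech Republic, Hungary, Italy, Spain and Sweden) will be included in the study". It adds: "A blocked randomization across the entire study (i.e. all sites as a whole) will be used". SAP 6.1.3 pools sites to country. Neither document gives country quotas, caps or expected shares.

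On sample size, SAP 6.1.4 states: "A sample size of 57 in each group will have 90% power to detect a treatment difference for change in severity of vaginal dryness". That calculation is for a plain Wilcoxon test without strata. After 18% dropout, "approximately 70 subjects/group have been finally estimated". SAP 6.3.1 adds: "The primary analyses will be performed using the ITT population using LOCF methodology".

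The dryness test is reused. For pH, SAP 6.3.1.2 says: "Model assumptions will be examined and, if required, a Wilcoxon Rank Sum test as described for vaginal dryness" is the fallback. SAP 6.3.1.3 and 6.3.1.4 do the same for the two cytology endpoints, and SAP 6.3.2 applies the test to the secondary symptom and sign scores.

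**The concern.** With SCORES = RANK, subjects are ranked within country and the raw rank sums are added. A rank sum from a large country is on a larger scale, so large countries count for more than their share of subjects. If the treatment effect is similar everywhere, this weighting is inefficient. Modified ridits divide each country's ranks by its size plus one, which makes the weights roughly proportional to size.

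Dryness is where spare power is scarcest: it needs 57 per arm, against 48 for pH, 24 for superficial cells and 9 for parabasal cells. Under SAP 6.3.1.5 a dose must succeed on all four endpoints before the next lower dose is tested. Power lost on dryness is therefore lost for the dose claim and for finding the minimal effective dose.

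**Working it through.** **Inputs.** From SAP Table 2, the proportions with change -3, -2, -1 and 0 are 0.189, 0.423, 0.270, 0.118 (estriol) and 0.118, 0.196, 0.353, 0.333 (placebo). The level is one-sided 0.025, with 57 per arm evaluable and 70 randomized. Country shares are assumed.

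**The plan's own figure.** P(estriol better) = 0.189×0.882 + 0.423×0.686 + 0.270×0.333 = 0.5468. P(tie) = 0.2398. So P(better) + ½P(tie) = 0.6667. The ordinal Wilcoxon formula with tie correction gives 90.6% power at 57 per arm, which matches the stated 90%. For dropout, 57/(1 − 0.18) = 69.5, so 70.

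**Weights and efficiency.** Let country h have N_h subjects. The estriol rank sum minus its null mean has expectation proportional to N_h² and variance proportional to N_h³.

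- RANK adds these deviations, so country h has weight N_h²/ΣN².
- MODRIDIT divides each by N_h + 1, so the weight is about N_h/ΣN.
- The efficiency of RANK relative to MODRIDIT is (ΣN²)² / (ΣN³ × ΣN).

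For 40/25/20/10/5, in shares: Σs² = 0.275 and Σs³ = 0.08875. The largest country's weight is 0.16/0.275 = 58%, and the efficiency is 0.275²/0.08875 = 0.85. For 50/20/15/10/5: Σs² = 0.325 and Σs³ = 0.1375. The weight is 0.25/0.325 = 77%, and the efficiency is 0.325²/0.1375 = 0.77.

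**Power by simulation.** Changes were drawn from Table 2, with country independent of arm, a stratified z with permutation variance, and 10,000 runs per cell (standard error at most 0.4 points). Entries are RANK vs MODRIDIT, %.

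| Country split | Efficiency | 70 per arm | 63 per arm | 57 per arm |
|---|---|---|---|---|
| Equal | 1.00 | 94.0 vs 94.5 | 90.6 vs 91.4 | 87.8 vs 88.9 |
| 30/25/20/15/10 | 0.92 | 92.3 vs 94.4 | 89.2 vs 91.9 | 85.4 vs 88.2 |
| 40/25/20/10/5 | 0.85 | 91.2 vs 94.6 | 87.8 vs 91.8 | 83.7 vs 88.8 |
| 50/20/15/10/5 | 0.77 | 88.8 vs 94.4 | 84.7 vs 91.6 | 81.4 vs 89.2 |

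The unstratified test at 57 per arm gives 89.9 to 90.7%. Repeating the table with 20,000 runs per cell agreed to within about 1 point. Other splits at 70 per arm (60,000 runs) gave 90.3 vs 94.4 for 40/25/15/12/8, 89.6 vs 94.5 for 50/25/15/5/5 and 87.0 vs 94.5 for 60/10/10/10/10.

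**Type I error**, with placebo proportions in both arms at 70 per arm: RANK 2.3 to 2.8%, MODRIDIT 2.2 to 2.8%.

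**Unequal effects**, 70 per arm, 2,500 runs (standard error at most 1.0 point). A partial effect means that this fraction of treated subjects follow the estriol profile and the rest the placebo profile.

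| Effect pattern | 40/25/20/10/5 | 50/20/15/10/5 |
|---|---|---|
| Largest country full, others half | 73 vs 68 | 80 vs 77 |
| Largest country full, others 75% | 84 vs 85 | 84.5 vs 88 |
| Largest country half, others full | 66 vs 81 | 48 vs 74 |

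**The case against.** The planned test is not an error. It meets the protocol's requirement, is pre-specified and holds its level.

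The 57-per-arm figures are a worst case. The primary analysis is ITT with LOCF, and Protocol 4.2.2 and 6.1.5 call for a final examination, including dryness, pH and smear, in treated women who stop early. Only women with no post-baseline dryness value drop out, so the analysed number should lie nearer 70. At 70 the planned test keeps at least 91% in three of the four splits. This stands, and the 70-per-arm column is the fairer guide. The margin is thin, though: at 68 per arm RANK gives 92.9, 91.6, 89.9 and 87.2%.

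The advantage of MODRIDIT needs a broadly similar effect across countries. If the effect in the largest country is twice that elsewhere, RANK is better. Repeat runs put that loss at about 3 points, against 3 and 5 in the table above. That is comparable to the 3.4-point gain in the 40/25/20/10/5 split, so it is not negligible. The reverse pattern favours MODRIDIT by 15 and 26 points, and nothing in the documents predicts a larger effect in the largest country.

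The reuse of the test adds little to the power argument. The pH and cytology fallback applies only if model assumptions fail. For pH at 70 per arm, with 77% efficiency and a Wilcoxon efficiency of 0.955 for normal data, the effective number is 70 × 0.77 × 0.955 = 51.5. Then (0.89/1.33) × √(51.5/2) − 1.96 = 1.43, or about 92% power. The secondary scores lie outside the gatekeeping. Consistency is the reason to extend the change to them.

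**Conclusion.** The concern holds as a matter of efficiency, not validity. With a common effect, RANK had lower power than MODRIDIT in every split examined. The four-split table shows a loss of 0.5 to 5.6 points at 70 per arm and 1.1 to 7.8 points at 57. At 70 per arm, only the most skewed of those four splits falls below 90%.

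These sizes rest on assumed country shares, on the Table 2 proportions and on a similar effect in each country. Dilution of the effect by LOCF is not modelled. The change is worth considering because it is cheap and concerns the endpoint that sets the sample size.

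**What to change.** Before unblinding, amend SAP 6.3.1.1 to use SCORES = MODRIDIT, stratified by country. For consistency, carry the change into the fallback analyses in 6.3.1.2 to 6.3.1.4 and the symptom and sign analyses in 6.3.2 that refer to 6.3.1.1. Keep the SCORES = RANK result as a sensitivity analysis. Country should remain the only stratum, because country-by-baseline-severity strata could be small. The Hodges-Lehmann estimates are already planned without country adjustment and do not change.

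The cost is one SAS option and, since the SAP is marked Final 1.0, a documented amendment. No new data are needed. There is almost no gain if countries enrol equally, and a loss of about 3 to 5 points if the effect is much larger in the largest country.

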6.3.1.2 Change from Baseline to Week 12 in Severity of Vaginal pH

A vaginal pH determination will be performed at the Screening, Week 3 and Week 12 / Early Termination visits.

The vaginal pH will be summarized using descriptive statistics for continuous variables by treatment and visit. The change from Baseline (Screening) value will also be summarized for all post-Baseline visits.

The mean change in vaginal pH from Baseline to the Week 12 / Early Termination visit will be analyzed using a parametric analysis of covariance (ANCOVA) model. The model will include treatment and country as fixed effects and the Baseline (Screening) pH will be used as a covariate. The adjusted (least-square) mean (LS Mean) change in vaginal pH from Baseline to Week 12 will be presented for each treatment, along with the corresponding SE. The difference in LS Means between treatment groups (0.005% Estriol versus Placebo, 0.002% Estriol versus Placebo and 0.0008% Estriol versus Placebo) will also be presented with 95% CI and one-sided p-value. The p-values for the model parameters of country and Baseline pH will also be presented. Model assumptions will be examined and, if required, a Wilcoxon Rank Sum test as described for vaginal dryness (Section 6.3.1.1) will be used. Missing values at Week 12 will be estimated using LOCF methodology for the ITT population analysis only. Only post-Baseline values will be carried forward.

6.3.1.3 Change from Baseline to Week 12 in Proportion of Superficial Cells of the Vaginal Epithelium

Vaginal smears will be performed at the Screening, Week 3 and Week 12 / Early Termination visits. Two vaginal smears will be collected per subject at each visit, with one cytological sample sent to the central laboratory [REDACTED] for analysis, and one sample retained at site for backup purposes. The samples sent to [REDACTED] will be evaluated by two different cytopathologists who will be blinded to subject, treatment assignment and to each other's evaluations. The number and percentage of superficial cells will be provided for each pathologist's cytologic evaluation, and the percentages will be converted to proportions for statistical presentation.

The proportion of superficial cells of a given subject and visit to be used for analysis will be derived as the mean result across the two pathologists. The evaluations of both pathologists must be verified by the Clinical Research Associate (CRA) in order to be considered for final analysis.

The proportion of superficial cells will be summarized using descriptive statistics for continuous variables by treatment and visit in a general summary table of vaginal cytology parameters. The change from Baseline (Screening) value will also be summarized for all post-Baseline visits.

The mean change in proportion of superficial cells from Baseline to the Week 12 / Early Termination visit will be analyzed using a parametric analysis of covariance (ANCOVA) model. The model will include treatment and country as fixed effects and the Baseline (Screening) proportion of superficial cells will be used as a covariate. The adjusted (least-square) mean (LS Mean) change in proportion of superficial cells from Baseline to Week 12 will be presented for each treatment, along with the corresponding SE. The difference in LS Means between treatment groups (0.005% Estriol versus Placebo, 0.002% Estriol versus Placebo and 0.0008% Estriol versus Placebo) will also be presented with 95% CI and one-sided p-value. The p-values for the model parameters of country and Baseline proportion of superficial cells will also be presented. Model assumptions will be examined and, if required, a Wilcoxon Rank Sum test as described for vaginal dryness (Section 6.3.1.1) will be used. Missing values at Week 12 will be estimated using LOCF methodology for the ITT population analysis only. Only post-Baseline values will be carried forward.

6.3.1.4 Change from Baseline to Week 12 in Proportion of Parabasal Cells of the Vaginal Epithelium

The proportion of parabasal cells is based on the evaluation of vaginal smears by two pathologists at [REDACTED] and the change from Baseline to Week 12 will be summarized and analyzed exactly as described for superficial cells in Section 6.3.1.3.

6.3.1.5 Gatekeeping Procedure

For the co-primary efficacy endpoints, a gatekeeping procedure will be employed. The 0.005% Estriol dose will be compared to placebo, and if this is significant at a one-sided alpha level of 0.025 for all four co-primary endpoints, then the 0.002% Estriol dose versus placebo can be considered. If this is also significant at a one-sided alpha level of 0.025 for all four co-primary endpoints, then the 0.0008% Estriol dose versus placebo can be considered. The approach to be taken is outlined in Table 4 below.

The one-sided p-values for all four co-primary endpoints will be presented for all three treatment comparisons in an overall gatekeeping table, so that it may be clearly seen whether or not all four co-primary endpoints are statistically significant and therefore be determined for which treatment comparisons efficacy can be formally declared. The overall gatekeeping table will be presented using the ITT population with LOCF methodology for the co-primary efficacy analyses, and also

using observed data only for the PP population and the ITT population in order to confirm the co-primary efficacy results.

Table 4: Gatekeeping Procedure for Efficacy Analyses

Test	Endpoints	All endpoints significant	Result	Next step
0.005% Estriol versus placebo	Vaginal dryness Vaginal pH Superficial cells Parabasal cells	Yes	If treatment difference exists between 0.005% Estriol and placebo, move to next dose	Continue to test 0.002% Estriol versus placebo
	Vaginal dryness Vaginal pH Superficial cells Parabasal cells		Not enough evidence to conclude a difference exists between 0.005% Estriol and placebo	Stop testing
0.002% Estriol versus placebo	Vaginal dryness Vaginal pH Superficial cells Parabasal cells	Yes	If treatment difference exists between 0.002% Estriol and placebo, move to next dose	Continue to test 0.0008% Estriol versus placebo
	Vaginal dryness Vaginal pH Superficial cells Parabasal cells		Not enough evidence to conclude a difference exists between 0.002% Estriol and placebo	Stop testing
0.0008% Estriol versus placebo	Vaginal dryness Vaginal pH Superficial cells Parabasal cells	Yes	Treatment difference exists between 0.0008% Estriol and placebo	Stop testing
	Vaginal dryness Vaginal pH Superficial cells Parabasal cells		Not enough evidence to conclude a difference exists between 0.0008% Estriol and placebo	Stop testing

